7.6.2 Serious Adverse Events and Adverse Event Leading to Discontinuation

Summaries of worst grade of on-study SAE, both by individual grade (1, 2, 3, 4, or 5, together with an Any Grade category) and by grade grouped as "Any, Grade 3-4 and Grade 5" will also be presented. This last summary will be repeated for:

- On-study drug-related SAEs
- On-study AEs leading to discontinuation.
- On-study Drug related AEs leading to discontinuation

By-subject listings of SAEs and AEs leading to study drug discontinuation will be produced for all treated subjects.

7.6.3 Adverse Events of Special Interest

7.6.3.1 Infusion Reactions

Infusion reaction is a known elotuzumab toxicity. Two different approaches will be taken when defining infusion reaction.

The first way of defining infusion reaction will be based on investigator assessment. An investigator reported infusion reaction will be any non-serious or serious adverse event judged by the investigator to be infusion related start on the day or the day after the elotuzumab infusion.

A second approach will be to create a composite term called "peri-infusional adverse event", which will be defined as any event from a pre-defined list of MedDRA terms (regardless of relationship to study drug) which starts on the day or the day after the elotuzumab infusion. See Appendix 2 for the list of preferred terms making up the composite term "peri-infusional adverse event". The list of terms making up "peri-infusional adverse event" is broad and is expected to over-estimate the true incidence of clinically meaningful infusion reaction.

Frequency tables of the worst grade of on-study investigator infusion reaction will be presented, both by individual grade (1,2,3,4 or 5, together with an Any Grade category) and by grade grouped as "Any, Grade 3-4 and Grade 5".

Worst grade for "peri-infusional adverse event" and "infusion reaction" will be presented, as Any, Grade 3-4 and Grade 5, only the preferred terms will be presented not the system organ class (SOC).

Listings for infusion reactions and peri-infusional adverse events will be provided.

7.6.3.2 Second Primary Malignancies

A summary table and by-subject listing of second primary malignancies will be provided. Information on secondary malignancies will be obtained from the on-treatment eCRF page for secondary malignancies and the "Survival Status" eCRF page.

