5. STUDY ASSESSMENTS AND PROCEDURES

5.1 Flow Chart/Time and Events Schedule

Table 5.1-1:Screening Procedural Outline (CA204142)								
Procedure	Screening Visit	Notes						
Eligibility Assessments								
Informed Consent	Х	Prior to any screening procedures						
Inclusion/Exclusion Criteria	Х	Within 14 days prior to first dose of study drug						
Medical History/Treatment History	Х							
Safety Assessments								
Physical Examination	Х	Includes height and weight within 14 days prior to first dose of study drug						
Vital Signs	Х	Temperature, BP, HR, within 14 days prior to first dose of study drug						
Performance Status (ECOG)	Х	Within 14 days prior to first dose of study drug						
Serious Adverse Events Assessment	Х	Collected from the time of informed consent						
Concomitant Medications	Х	Within 14 days prior to first dose of study drug						
ECG	Х	Within 28 days of randomization						
Laboratory Assessments	•	•						
CBC, differential, platelets	Х	Within 14 days prior to first dose of study drug						
Chemistry	Х	Within 14 days prior to first dose of study drug (See Section 5.3.4)						
Serum β2-microglobulin	Х	Within 28 days prior to first dose of study drug (Central Lab Analysis)						
Albumin	Х	Within 28 days prior to first dose of study drug						
Pregnancy Test	Х	For WOCBP only, 2 pregnancy tests, one 10 - 14 days prior to start of study drug and one within 24 hours prior to start of study drug. Urine tests must have a sensitivity of at least 25 IU/L.						
Thyroid Function Tests (TFTs) (reflex to free T3/total T3, free T4 for abnormal TSH result).	X	Within 28 days prior to first dose of study drug. Required only after Amendment 02.						

Table 5.1-1:Screening Procedural Outline (CA204142)								
Procedure	Screening Visit	Notes						
Hepatitis B surface antigen (HBsAg), and hepatitis C antibody (HCV Ab) or HCV ribonucleic acid (RNA).	Х	Within 28 days prior to first dose of study drug. Required only after Amendment 02.						

Table 5.1-2:CA204142 Cycles 1 and 2 - EPd Cohort Only

Procedure	Day 1	Day 8	Day 15	Day 22	Rest Days 23 – 28	Notes			
Safety Assessments									
Targeted Physical Examination	Х					Perform prior to dosing, include weight			
Vital Signs	Х	X	Х	Х		Cycle 1: Measure vital signs pre-elotuzumab infusion, 30 minutes after the start of elotuzumab infusion, at the end of infusion, and 30 minutes after the completion of infusion Cycle 2 and beyond: evaluate prior to dosing			

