Performance Status (ECOG)	Х					Evaluate prior to dosing			
Serious Adverse Event Assessment	Х	Х	Х	Х		Evaluate prior to dosing			
Adverse Events Assessment	Х	Х	Х	Х		Evaluate prior to dosing			
Concomitant Medications	Х	Х	Х	Х		Evaluate prior to dosing			
Laboratory Tests	•			•					
CBC, differential, platelets	Х	X	Х	X		Can be drawn up to 3 days prior to study visit (See Section 5.3.4). Screening results are sufficient for Cycle 1			
Chemistry	Х					Can be drawn up to 3 days prior to study visit			
Pregnancy Test	Х	X			For WOCBP only. Urine tests must have a sensitivity of at least 25 IU/L. Test within 24 hours of Dose 1 study medication.				
Efficacy Assessments									
Myeloma Urine and Serum Lab tests	(Central Lab Analysis) Every 4 weeks from date of first dose of study drug until disease progression			b Analys s from d drug un ession	sis) ate of til disease	 Day 1 of each cycle (except Cycle 1 - refer to Screening visit for defined window as listed on Table 5.1-1) (See also: Section 5.4.2) 24-hour urine sample can be collected within ± 7 days of visit, and must be obtained in all subjects who have measurable UPEP M protein (≥ 200 mg/24 hours) at baseline with each cycle. 			
				See Section 5.4.2 for subjects without measurable urine M protein at baseline and no FLC detected by the serum test.					

Table 5.1-2:CA204142 Cycles 1 and 2 - EPd Cohort Only

Procedure	Day 1	Day 8	Day 15	Day 22	Rest Days 23 – 28	Notes
Bone Marrow Aspiration/Biopsy	For confirmation of CR if applicable or, if clinically indicated at time of suspected disease progression		plicable or, of suspected n	Bone marrow aspirate is mandatory. Bone marrow biopsy is optional. Bone marrow will be analyzed in local laboratory, with performance of IHC and/or flow cytometry to assess for sCR.		
Skeletal Imaging		If c	linically	indicat	ed	
CT/MRI assessment	As clinically indicated					
Response per IMWG uniform criteria	Every 4 weeks from date of first dose of study drug on Cycle 1 Day 1 until progression. (Cycles cannot be delayed. In the event that the first dose within a cycle is delayed or omitted, the tumor assessment should still be done on Day 1 of the cycle and should not be delayed until dosing.).					Subjects who discontinue from study treatment for reasons other than progression will continue to have tumor assessment every 4 weeks from C1D1 until progression.

Table 5.1-3:CA204142 Cycles 3 and Beyond - EPd Cohort and Cross-over Patients from EN Cohort

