Procedure	Day 1	Day 8	Day 15	Day 22	Rest Days 23 - 28	End of Treatment	Days 30 & 60 post end of treatment*	Notes
Safety Assessments				•			·	
Targeted Physical Examination	Х							Perform prior to dosing, includes weight
Vital Signs	Х					Х		Evaluate prior to dosing.
Performance Status (ECOG)	Х					Х		Evaluate prior to dosing
Serious Adverse Event Assessment	Х					Х	Х	Evaluate prior to dosing SAEs will be collected for EPd subjects up to 100 days of last dose (per Section 6.1.1).
Adverse Events Assessment	Х					Х	Х	Evaluate prior to dosing
Concomitant Medications	Х					Х	Х	Evaluate prior to dosing
Laboratory Tests				.			•	
CBC, differential, platelets	Х					Х		Can be drawn up to 3 days prior to visit. Additional samples as clinically indicated.
Chemistry	Х					Х		Can be drawn up to 3 days prior to visit (See Section 5.3.4)
Pregnancy Test	Х					X	X	For WOCBP only. Tests must occur within 24 hours prior to dosing. The pregnancy test should occur on Days 1 of each cycle. Urine tests must have a sensitivity of at least 25 IU/L. Pregnancy test must also be performed at end of treatment and at 30, 60 and 90 days off treatment. The test at 90 days off treatment may be performed locally if the patient is not scheduled to return to the center for other reasons.

Table 5.1-3:	CA204142 Cycles 3 and Beyond - EPd Cohort and Cross-over Patients from EN Cohort
--------------	--

Procedure	Day 1	Day 8	Day 15	Day 22	Rest Days 23 - 28	End of Treatment	Days 30 & 60		
							post end of treatment*	Notes	
Efficacy Assessments									
Myeloma Urine and Serum Lab tests				(Ce Every	ntral Lab An 4 weeks fror	alysis) n date of		Day 1 of each cycle (except Cycle 1 - refer to Screening visit for defined window).	
		fir	st dose	of stud	ly drug until o	disease progres	sion	24-hour urine sample can be collected within ± 7 days visit and must be obtained in all subjects who have measurable UPEP M protein (≥ 200 mg/24 hours) a baseline with each cycle.	
								See Section 5.4.2 for subjects without measurable urine M protein at baseline and no FLC detected by the serum test.	
Bone Marrow Aspiration/Biopsy	For co	onfirma	tion of of	CR if a f suspe	applicable or, cted disease j	if clinically in orogression	dicated at time	Bone marrow aspirate is mandatory. Bone marrow biopsy is optional.	
								Bone marrow will be analyzed in local laboratory, with performance of IHC and/or flow cytometry to assess for sCR.	

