Corrected calcium	Eve dise	ery 4 we ease pro	eeks fro ogressic t	om the on, rega herapy	date of the fi ardless of who or subsequen	rst dose of stud ether the subjec nt therapy.	y drug until t is on study	Serum calcium and albumin from peripheral blood at D1 of each cycle until disease progression, even if subject is on subsequent therapy; if used as criterion for disease progression, must be confirmed by second value.	
Skeletal Imaging				If	clinically ind	cated			
CT/MRI assessment				As	clinically ind	icated			

Table 5.1-3: CA204142 Cycles 3 and Beyond - EPd Cohort and Cross-over Patients from EN Cohort

Procedure	Day 1	Day 8	Day 15	Day 22	Rest Days 23 - 28	End of Treatment	Days 30 & 60 post end of treatment*	Notes
Response per IMWG uniform criteria	Every until p dos shoul	4 week rogress se withi d still t	cs from sion. (C in a cyc be done	date o ycles c le is de on Da	f first dose of annot be dela alayed or omi y 1 of the cyc until dosing.	study drug on yed. In the eve itted, the tumor ele and should n .).	Cycle 1 Day 1 nt that the first assessment not be delayed	Subjects who discontinue from study treatment for reasons other than progression will continue to have tumor assessment every 4 weeks from C1D1 until progression. Following disease progression, subjects will be followed at least annually for survival.

* Subjects in the EN cohort who cross-over to the EPd cohort but discontinue treatment within 2 cycles of EPd treatment will still need to undergo 100 day followup visit from last dose of nivolumab to evaluate safety events related to study treatment.

Table 5.1-4:CA204142 Cycles 1 and 2 - EN Cohort

Procedure	Day 1	Day 8	Day 15	Day 22	Rest Days 23 – 28	Notes
Safety Assessments						
Targeted Physical Examination	Х					Perform prior to dosing, include weight
Vital Signs	Х	X	Х	X		Cycle 1: Measure vital signs pre-elotuzumab infusion, 30 minutes after the start of elotuzumab infusion, at the end of infusion, and 30 minutes after the completion of infusionCycle 2 and beyond: Evaluate prior to dosing.Vital signs must be collected if infusion related AE occurs.
Performance Status (ECOG)	Х					Evaluate prior to dosing
Serious Adverse Event Assessment	Х	X	Х	X		Evaluate prior to dosing
Adverse Events Assessment	Х	Х	Х	X		Evaluate prior to dosing
Concomitant Medications	Х	X	Х	X		Evaluate prior to dosing
Second Primary Malignancy	Х					
Laboratory Tests						

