6.1 Serious Adverse Events

A Serious Adverse Event (SAE) is any untoward medical occurrence that at any dose:

- results in death
- is life-threatening (defined as an event in which the subject was at risk of death at the time of the event; it does not refer to an event which hypothetically might have caused death if it were more severe)
- requires inpatient hospitalization or causes prolongation of existing hospitalization (see **NOTE** below)
- results in persistent or significant disability/incapacity
- is a congenital anomaly/birth defect

• is an important medical event (defined as a medical event(s) that may not be immediately lifethreatening or result in death or hospitalization but, based upon appropriate medical and scientific judgment, may jeopardize the subject or may require intervention [eg, medical, surgical] to prevent one of the other serious outcomes listed in the definition above.) Examples of such events include, but are not limited to, intensive treatment in an emergency room or at home for allergic bronchospasm; blood dyscrasias or convulsions that do not result in hospitalization.) Potential drug induced liver injury (DILI) is also considered an important medical event. (See Section 6.6 for the definition of potential DILI.)

Suspected transmission of an infectious agent (eg, pathogenic or nonpathogenic) via the study drug is an SAE.

Although pregnancy, overdose, cancer, and potential drug induced liver injury (DILI) are not always serious by regulatory definition, these events must be handled as SAEs. (See Section 6.1.1 for reporting pregnancies).

Any component of a study endpoint that is considered related to study therapy (eg, death is an endpoint, if death occurred due to anaphylaxis, anaphylaxis must be reported) should be reported as SAE (see Section 6.1.1 for reporting details).

NOTE:

The following hospitalizations are not considered SAEs in BMS clinical studies:

- a visit to the emergency room or other hospital department < 24 hours, that does not result in admission (unless considered an important medical or life-threatening event)
- elective surgery, planned prior to signing consent
- admissions as per protocol for a planned medical/surgical procedure
- routine health assessment requiring admission for baseline/trending of health status (eg, routine colonoscopy)
- medical/surgical admission other than to remedy ill health and planned prior to entry into the study. Appropriate documentation is required in these cases

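### The second-primary-malignancy table omits SAE records as a source, so EPd and crossover malignancies may be missing from it, and scheduled ascertainment differs by cohort

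*SAP*

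**What the plan says.** SAP 7.6.3 lists two adverse events of special interest, infusion reactions and SPMs. For the SPM table and listing, section 7.6.3.2 reads: "Information on secondary malignancies will be obtained from the on-treatment eCRF page for secondary malignancies". It then adds the Survival Status page. It names no AE or SAE records and no reconciliation step.

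In Protocol 5.1, "Second Primary Malignancy" is a scheduled row in the three EN tables: Day 1 of each cycle in Tables 5.1-4, 5.1-5 and 5.1-6, with end of treatment and Days 30 and 100 added in Table 5.1-6. The row does not appear in Table 5.1-2 ("CA204142 Cycles 1 and 2 - EPd Cohort Only") or in Table 5.1-3 ("CA204142 Cycles 3 and Beyond - EPd Cohort and Cross-over Patients from EN Cohort").

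Protocol 6.1 sets the reporting rule for every subject: "Although pregnancy, overdose, cancer, and potential drug induced liver injury (DILI) are not always serious by regulatory definition, these events must be handled as SAEs". Section 6.1.1 collects SAEs until 100 days after dosing stops.

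**The concern.** The SPM table depends on a page whose matching visit item is scheduled for one cohort only. In EPd subjects, and in EN subjects once they cross over, the documented way for an on-treatment cancer to enter the database is an SAE report. The SAP does not use that source for this table. Followed as written, the plan can leave a cancer out of the special-interest table while it sits in the SAE data.

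EPd is the larger cohort, with at least 60 treated against about 30 in EN. At these sizes the table will hold few events, so one absent case changes what a reader takes from it. A reported zero is the most exposed result.

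**Working it through.** The documents give no SPM rate or count, so there is no stated figure to reproduce. The check is a comparison of the sections, followed by an illustration under assumed values.

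**Sources side by side**

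| Item | EN before crossover | EPd, and EN after crossover |
|---|---|---|
| Scheduled SPM row | Tables 5.1-4, 5.1-5, 5.1-6 | None visible in Tables 5.1-2, 5.1-3 |
| Cancer handled as an SAE (Protocol 6.1) | Yes | Yes |
| SAE collection to 100 days (Protocol 6.1.1) | Yes | Yes |
| Survival follow-up, at least annually after progression (Protocol 3.1) | Yes | Yes |
| SAE records feed the SPM table (SAP 7.6.3.2) | Not named | Not named |

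Four things follow.

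1. The cohorts differ in the scheduled row and not in the SAE rule. For an EN subject the scheduled assessment stops at crossover, because Table 5.1-3 then applies.
2. General AE questioning is not equivalent to the scheduled item. Protocol 6 calls for open-ended elicitation and says that subjects should not be asked about specific events.
3. The Survival Status page is open to both cohorts in principle. However, survival follow-up is described as starting after progression, by phone and at least yearly (Protocol 3.1 and 5.4.1), and neither document ties the page to an on-treatment visit.
4. The SAE summaries in SAP 7.6.2 cover on-study events, which SAP 7.6.1 ends 60 days after the last dose. SAEs from day 61 to day 100 are collected but fall outside those summaries. The SAP states no such cut-off for the by-subject SAE listing.

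**Size of one case**

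- EPd: 1/60 = 1.7 percentage points. EN: 1/30 = 3.3 percentage points.
- A zero in 60 would carry an exact 95% upper limit of 1 − 0.025^(1/60) = 6.0%.

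**Illustration for EPd, N = 60.** Let p be the true SPM risk and c the share of cases that reach the two named pages. Neither is in the documents; both are assumed. Expected cases tabulated = N × p × c, and P(none tabulated) = (1 − p × c)^N.

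| p | c | Expected cases | Expected tabulated | P(none tabulated) |
|---|---|---|---|---|
| 5% | 100% | 3.0 | 3.0 | 0.046 |
| 5% | 75% | 3.0 | 2.25 | 0.101 |
| 5% | 50% | 3.0 | 1.5 | 0.219 |
| 5% | 25% | 3.0 | 0.75 | 0.470 |
| 2% | 50% | 1.2 | 0.6 | 0.547 |
| 8% | 50% | 4.8 | 2.4 | 0.086 |

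With c = 100% nothing is lost. The table shows how the loss would scale, not that one occurs.

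**The case against.** The strongest reply is that no loss has been shown. SAP 7.6.3.2 attaches no cohort restriction to the malignancy page, and an absent visit row does not prove absent collection. Table 5.1-2, for example, has no corrected-calcium row, yet calcium and albumin are in the chemistry panel of Table 5.3.4-1. The Survival Status page is a second source for both cohorts. EPd subjects have AE and SAE assessments at every scheduled dosing visit in Cycles 1 and 2, then on Day 1 of each cycle, at end of treatment and at Days 30 and 60. A malignancy with onset up to 60 days after the last dose would appear in the AE and SAE tables whatever the SPM table shows. The cohorts are non-randomised, differ in prior lines (one or two against at least four) and are analysed separately under SAP 7.1.

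All of this stands, and it rules out several stronger readings that a reader might infer:

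- That EPd malignancies are under-counted, or that the EPd rate is biased low. The documents do not settle whether the page is completed for EPd.
- That SAE handling of cancer is what separates the cohorts. The rule covers the whole study.
- That cases are lost to the study. At issue is one table and its listing.
- That a planned cohort comparison is invalid. None is planned.

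The reply does not remove the gap itself. The SAP leaves out the one source that the protocol requires for every reported cancer, and it does not say how a conflict between the SPM table and the SAE listing would be resolved.

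**Conclusion.** The point holds as a completeness risk in one special-interest safety table. EPd and crossover malignancies may be missing from the SPM table, and scheduled ascertainment differs between EN subjects and those on EPd. Each missing case is worth 1.7 points in EPd. The total effect cannot be calculated from the documents and is nil if every case reaches the two pages.

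The conclusion assumes that the visible Tables 5.1-2 and 5.1-3 are complete. A redacted SPM row cannot be fully excluded, but it is unlikely because the same row is visible in all three EN tables. Even if the row were present, the omission of SAE records from SAP 7.6.3.2 would remain. No efficacy result is affected.

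**What to change.** Amend SAP 7.6.3.2 in three ways.

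1. Define SPMs in both cohorts as the union of the malignancy page, the Survival Status page and all AE/SAE records coded to a new malignancy with onset after first dose. Identify the coded records by a MedDRA malignancy search, include SAEs collected to 100 days, and de-duplicate to one count per subject and malignancy.
2. State whether the malignancy page applies to EPd subjects and to EN subjects after crossover.
3. Footnote the table with the difference in scheduled ascertainment.

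The cost is minor programming on data already collected and a review of the coded terms, so that myeloma progression is not counted as a new malignancy. The SAP already uses a MedDRA term list for its other special-interest event (Appendix 2).

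Adding an SPM row to Tables 5.1-2 and 5.1-3 is not needed. EPd enrollment is closed, the change would require a protocol revision with ethics approval, and it would make ascertainment vary over time within EPd.

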7.6.4 Deaths

The number and percentage of deaths and the investigator-reported cause of death will be presented. This will be summarized for all deaths, and for those reported on study treatment or within 60 days of discontinuing study treatment.

A by-subject listing will be provided and will present date of death and reason of death.

7.6.5 Clinical Laboratory Evaluations

On-treatment laboratory tests for safety are defined as those that occur after first dose of any study therapy until 60 days after last dose of any study therapy.

The number and percentage of subjects with each worst severity grade for on-study hematology parameters (hemoglobin, WBC, ANC, ALC and platelets) will be presented. Grades will be categorized as Grade 1, Grade 2, Grade 3, Grade 4, Any Grade and Grade 3-4. Subjects will be counted only once for each parameter, according to their worst post baseline CTC grade. The percentage of subjects with each worst severity grade will be calculated out of the number of all treated subjects with on-study assessment for lab parameter. Subjects without post-baseline (on-treatment) assessment for a lab parameter will be reported in the "NOT REPORTED" category.

This summary will be repeated for:

- Liver parameters (ALT, AST, alkaline phosphatase, albumin and total bilirubin) with available CTC grades
- Renal/electrolyte parameters (sodium, potassium, bicarbonate, calcium, glucose and creatinine) with available CTC grades

Sodium, potassium, calcium, and random glucose will be presented separately, based on their high and low values.

For blood urea nitrogen (BUN), direct bilirubin and total protein the worst category on-treatment will be presented. Results will be categorized as; below upper normal limits, above upper normal limits or not reported.

For reporting purposes, urea will be converted to BUN, using the conversion factor: urea (mmol/L) / 0.357 = BUN (mg/dL)."

Subjects experiencing any potential drug induced liver injury (DILI) will be summarized by treatment group and overall as follows:

• A summary of the number and percentage of subjects with (AST or ALT > 3 x upper limit of normal (ULN)) and (Total bilirubin > 2 x ULN and ALP < 2 x ULN) will be presented.

If any potential cases of DILI are identified then clinical review will be conducted to ensure no other immediate apparent possible causes of AT elevation and hyperbilirubinemia are present, including but not limited to, viral hepatitis, pre-existing chronic or acute liver disease, or the administration of other drugs known to be hepatotoxic.

Note: The timing for total bilirubin rising to $> 2 \times ULN$ needs to be concomitant with or within 30 days after ALT or AST rising to $> 3 \times ULN$. ALP needs to be $< 2 \times ULN$ at the time of or

within 2 weeks before ALT or AST rising to > 3 x ULN or TBILI > 2 x ULN. This means a normal ALP value (\leq 2 x ULN) must be present within 2 weeks of either the ALT/AST criteria or the TBILI criteria.

A by subject listing of all laboratory data will be provided for all treated subjects. A separate listing will be provided for all subjects potentially experiencing DILI. A by subject listing of pregnancy test data will also be provided.

